Where possible, triamcinolone cream 0.1% and/or hydrocortisone 2.5% ointment will be supplied by the sponsor for use as background TCS up to Week 104 (Visit 22). In the event of these specific TCS being unavailable, an alternate, equivalent-potency TCS may be provided by the sponsor (see below). Topical corticosteroid use, when supplied by the sponsor, should be recorded via weight of dispensed and returned tubes as indicated in the Schedule of Activities (Section 2). In the event that the sponsor is unable to supply TCS, commercially available triamcinolone 0.1% cream and/or hydrocortisone 2.5% ointment may be supplied by the sites.

- Where providing triamcinolone 0.1% cream and/or hydrocortisone 2.5% ointment is not possible, an equivalent-potency TCS cream and/or ointment that is in line with local practices can be supplied by the sites. Refer to [Appendix 7](#) for guidance on potency equivalence.
- Where possible, TCS use when supplied by the site should also be recorded via weight of dispensed and returned tubes, as indicated in the Schedule of Activities (Section 2); however, where this is not practical, this information does not need to be recorded, and will not be considered a protocol violation.
- If the TCS supplied by the sponsor is not considered suitable for an individual patient, an equivalent-potency TCS cream and/or ointment that is in line with local practices can be supplied by the sites. Refer to [Appendix 7](#) for guidance on potency equivalence.

Choice of High- and Ultra-High-Potency Topical Corticosteroids for Rescue

The use and choice of specific high- or ultra-high-potency TCS for rescue is at the discretion of the investigator and it will not be provided by the sponsor. The weights of dispensed and returned tubes of the high- and ultra-high-potency TCS are not required.

Other Topical Treatments

Investigators may also select to use TCIs and/or crisaborole in countries where approved, in place of TCS. If TCIs or crisaborole are prescribed, use should be limited to problem areas (e.g., face, neck, skin folds, genital areas, etc.).

Use of all topical treatments for AD must be recorded in the CRF.

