7.7.5. Rescue Therapy

Investigators should make every attempt to conduct efficacy and safety assessments immediately before administering any rescue treatment. An unscheduled visit should be used for this purpose if necessary.

7.7.5.1. Rescue during Period 2: Week 0 (Visit 2) up to Week 52 (Visit 14)

Control of AD symptoms should be attempted by avoiding exacerbating factors, intensifying emollient applications, and using only the permitted study treatments, including background TCS therapy (e.g., triamcinolone 0.1% cream and/or hydrocortisone 2.5% ointment) (see Section [7.7.2](#)).

Rescue with High- and Ultra-High-Potency TCS

Patients whose lesions persist or worsen despite the use of emollients and background TCS therapy (e.g., triamcinolone 0.1% cream and/or hydrocortisone 2.5% ointment) and/or patients who require prolonged applications of triamcinolone 0.1% cream (moderate-potency TCS) on large surfaces may be considered for rescue to high- or ultra-high-potency TCS (see [Appendix 7](#) for TCS potency).

High- or ultra-high-potency TCS may be used once daily for up to 14 consecutive days or based on the maximum duration recommended in the prescribing information.

It is recommended that if a patient reaches “clear” to “almost clear” skin after topical rescue, then high- or ultra-high-potency TCS should be stopped, and low- and/or moderate-potency TCS (e.g., triamcinolone 0.1%, hydrocortisone 2.5% ointment) should be used once daily for an additional 7 days, then stopped.

Patients rescued with high- or ultra-high-potency TCS will continue to take investigational product and use of topical rescue therapy will be documented in the eCRF.

Rescue with Phototherapy

Patients may also be rescued with phototherapy at the discretion of the investigator. Patients rescued with phototherapy will remain in the study and be required to temporarily interrupt use of investigational product until completion of the phototherapy (see Section [8.1.1](#) for Temporary Interruption of Investigational Product).

Rescue with Systemic Therapies

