**4.2.2. Other Secondary Objectives**

Other Secondary These are prespecified objectives that will not be adjusted for multiplicity	
Objectives	Endpoints
To test the hypothesis that baricitinib 4-mg + TCS, baricitinib 2-mg + TCS, or baricitinib 1-mg + TCS is superior to placebo + TCS in the treatment of moderate-to-severe AD	
 
Proportion of patients achieving IGA of 0 or 1 with a <math>\geq 2</math>-point improvement at Week 4 and Week 52
 
Proportion of patients achieving EASI75 at Week 4 and Week 52
 

To compare the efficacy of baricitinib 4-mg + TCS, baricitinib 2-mg + TCS, or baricitinib 1-mg + TCS to placebo + TCS in AD during the double-blind placebo-controlled treatment period as measured by improvement in signs and symptoms of AD	
 
Proportion of patients achieving EASI50 at 16 weeks
 
Proportion of patients achieving IGA of 0 at 16 weeks
 
Mean change from baseline in SCORAD at 16 weeks
 
Proportion of patients achieving SCORAD90 at 16 weeks
 
Mean change from baseline in BSA affected at 16 weeks
 
Proportion of patients developing skin infections requiring antibiotic treatment by Week 16
 
Mean number of days without use of background TCS over 16 weeks
 
Mean gram quantity of background TCS used over 16 weeks (tube weights)
 

To compare the efficacy of baricitinib 4-mg + TCS, baricitinib 2-mg + TCS, or baricitinib 1-mg + TCS to placebo + TCS in AD during the double-blind placebo-controlled treatment period as assessed by patient-reported outcome measures	
 
Percent change from baseline in Itch NRS at Week 52, Week 24, Week 16, Week 4, and Week 1
 
Proportion of patients achieving a 4-point improvement in Itch NRS at 24 weeks
 
Mean change from baseline in the total score of the POEM at 16 weeks
 
Mean change from baseline in the PGI-S-AD scores at 16 weeks
 
Mean change from baseline in HADS total scores at 16 weeks
 
Mean change from baseline in the DLQI total scores at 16 weeks
 
Mean change from baseline in the WPAI-AD total scores at 16 weeks
 
Mean change from baseline in the EQ-5D-5L total scores at 16 weeks
 

Substudy: Randomized Downtitration These are prespecified objectives that will be not be adjusted for multiplicity	

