- Proportion of patients achieving a  $\geq 4$ -point improvement in POEM total score for those with a baseline total score  $\geq 4$

HADS (including Week 52):

- Proportion of patients achieving a HADS Anxiety Score  $< 8$  for those with a baseline HADS Anxiety Score  $\geq 8$
- Proportion of patients achieving a HADS Depression Score  $< 8$  for those with a baseline HADS Depression Score  $\geq 8$
- Proportion of patients achieving improvement in HADS Anxiety Score or HADS Depression Score  $< 8$  for those with a baseline HADS Anxiety Score  $\geq 8$  or a baseline HADS Depression Score  $\geq 8$
- Change from baseline in HADS total score

BSA at Week 52:

- Mean change from baseline in BSA affected

Itch NRS at Week 52:

- Proportion of patients achieving a 4-point improvement in Itch NRS

Skin infections at Week 52:

- Proportion of patients developing skin infections requiring antibiotic treatment

Mean number of days without use of background TCS over 52 weeks

Mean gram quantity of background TCS used over 52 weeks (tube weights)

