### 6.3. Handling of Dropouts or Missing Data

Intercurrent events (ICH E9 R1) are events which occur after the treatment initiation and make it impossible to measure a variable or influence how it would be interpreted.

Depending on the estimand being addressed, different methods will be used to handle missing data as a result of intercurrent events. Intercurrent events may occur through the following:

- application of one of the censoring rules (including after permanent study drug discontinuation, after rescue therapy, or re-treatment)
- discontinuation of inadvertently enrolled patients

- discontinuation from the study due to enrollment in other trials, medical, safety or regulatory reasons, investigator decision, and patient decision
- missing an intermediate visit prior to discontinuation, rescue, or re-treatment
- loss to follow-up

Noncensor intercurrent events are events that are not due to the application of any censoring rule, that is, the last 4 items in the list above.

Note that as efficacy and health outcome data can accrue after a patient permanently discontinues study drug or begins rescue therapy, specific general censoring rules to the data will be applied to all efficacy and health outcome observations subsequent to these events depending on the estimand being addressed. These specific censoring rules are described below.

The *primary censoring rule* will censor efficacy and health outcome results after permanent study drug discontinuation or after rescue therapy. This censoring rule will be applied to all continuous and categorical efficacy and health outcome endpoints.

A *secondary censoring rule* will only censor efficacy and health outcome results after permanent study drug discontinuation. As a consequence, data for patients rescued with high or ultra-high potency TCS or with phototherapy will not be censored at the time of rescue as they can continue or only temporarily interrupt study drug. As patients who are rescued to systemic corticosteroids are required to permanently discontinue study drug, they will also have post-rescue observations censored. The secondary censoring rule will be applied to primary and key secondary efficacy and health outcome endpoints. The secondary censoring rule will be applied to all endpoints at Week 52 as the main analyses.

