## 6.8. Background Therapy

Throughout the study, background TCS therapy (for example, triamcinolone 0.1% cream and/or hydrocortisone 2.5% ointment) are to be used on active lesions (see JAIN protocol Section 7.7.2).

- Mean number of days without use of background TCS over 16 weeks and 52 weeks

The following analyses will be performed: The total number of days that the patients did not use background TCS will be summarized by both potencies throughout the entire 16-week treatment period and 24-week treatment period for 24-week interim analysis, and the entire 52-week treatment period for 52-week interim analysis. For 24-week interim analysis, the main analysis applies censoring rule #1. After patients who are rescued or discontinue investigational products, it is assumed that background TCS would be applied each day. In case of missing values in the daily diary, it will be assumed that background TCS has been used. Analysis will be done for Week 16 via ANOVA, with geographic region, baseline disease severity, and treatment as factors in the model. A secondary analysis will apply censoring rule #2, with the same assumptions for missing values as described above. For 52-week interim analysis, analysis will be done via ANOVA, with geographic region, baseline disease severity, and treatment as factors in the model.

- Mean number of days without use of background TCS in Period 3/4

Mean of the number of days that the patients did **not** use background TCS will be summarized for Long-Term Extension Period 3 (Week 52 through Week 68). Only descriptive statistics will be provided without using the censoring rule.

- Mean gram quantity of background TCS used over 16 weeks and 52 weeks, Week 52 through Week 104 (tube weights)

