Note: As rescue TCS (high/ultra-high potency) is not weighed, an analysis similar to the main analysis described above for the number of days without background TCS cannot be performed. Whether any background TCS is used for each patient is also collected in the diary device each day starting from the first dose date throughout the study.

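### Under censoring rule #2, a rescue-steroid day with no background TCS counts as a favourable day in the analysis of days without background TCS, including at Week 52

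*SAP*

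**What the plan says.** SAP 4.2.2 lists "Mean number of days without use of background TCS over 16 weeks" among the other secondary endpoints, which are not adjusted for multiplicity. SAP 4.3 adds an exploratory version, "Mean number of days without use of background TCS over 52 weeks".

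SAP 6.8 describes the analyses:

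- **Week 16, main (rule #1).** Once a patient is rescued or stops study drug, background TCS is taken as used on every later day. A missing diary day is also taken as use.
- **Week 16, secondary (rule #2).** "A secondary analysis will apply censoring rule #2, with the same assumptions for missing values as described above".
- **Week 52.** Only an ANOVA and its factors are given. No censoring rule, rescue convention or missing-diary convention is stated.

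The rule for Week 52 has to be taken from SAP 6.3: "The secondary censoring rule will be applied to all endpoints at Week 52 as the main analyses". That section also says that under rule #2 "data for patients rescued with high or ultra-high potency TCS or with phototherapy will not be censored at the time of rescue".

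On data capture, the closing note of SAP 6.8 says the daily diary records whether background TCS was used. It gives as a limitation: "As rescue TCS (high/ultra-high potency) is not weighed". Protocol 7.7.2 likewise does not require rescue tubes to be weighed, but it does say: "Use of all topical treatments for AD must be recorded in the CRF". On duration, Protocol 7.7.5 says: "High- or ultra-high-potency TCS may be used once daily for up to 14 consecutive days", or the maximum in the prescribing information.

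**The concern.** Rescue to a stronger topical steroid is given because lesions persist or worsen. If a patient sets the background product aside while using the rescue product, the diary shows no background use and rule #2 leaves those days in the analysis. An escalation of topical steroid treatment then scores as benefit on an endpoint listed under improvement in signs and symptoms.

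The two time points can also differ in meaning. The Week 16 main result never credits a post-rescue day. The Week 52 main result, read with SAP 6.3, can. A reader comparing the two would be comparing different conventions as well as different durations.

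**Working it through.** The documents state no expected value for this endpoint, so there is no plan figure to reproduce. The check sets the rules side by side and then bounds the effect.

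**Step 1. How one rescue day is scored**

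| Situation on a rescue-TCS day | Rule #1 | Rule #2 |
|---|---|---|
| Background TCS also applied | use | use |
| Diary entry missing | use | use (convention carried over at Week 16; not stated for Week 52) |
| Diary says no background TCS | use | **day without background TCS** |

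Only the last row differs. The rule #2 sentence for days carries over assumptions about missing values. A diary answer of no background use is an observed value, so nothing in the text overrides it.

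**Step 2. Effect per rescued patient**

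Periods: 16 × 7 = 112 days and 52 × 7 = 364 days. Let *s* be the share of rescue days on which no background TCS was applied (0 to 1). For one full 14-day course the number of days moved is 14 × *s*, that is 0 to 14.

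- Week 16: 14 / 112 = 12.5% of the period at most.
- Week 52: 14 / 364 = 3.8% of the period at most.
- *s* = 0: no effect.

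As an example, take rescue at day 56 of 112 with one full course and the 7-day step-down to low- or moderate-potency TCS recommended in Protocol 7.7.5. Rule #1 allows 0 favourable days afterwards. Rule #2 allows up to 14 rescue days plus any observed background-free days among the remaining 112 − 56 − 14 − 7 = 35. The 7 step-down days count as use if the product is applied. Only the 14 rescue days are at issue. Background-free days among the 35 are real ones, unless further rescue TCS is used.

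**Step 3. Shift in the difference between arms**

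Shift in mean days per patient = *d* × *k* × 14 × *s*, where *d* is the difference between arms in the proportion rescued and *k* is the number of 14-day courses per rescued patient. The documents give none of *d*, *k* or *s*, so all three are assumed.

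| Time | *d* | *k* | *s* | Shift (days) | % of period |
|---|---|---|---|---|---|
| Week 16 | 0.20 | 1 | 0 | 0 | 0 |
| Week 16 | 0.20 | 1 | 0.5 | 1.4 | 1.25 |
| Week 16 | 0.20 | 1 | 1 | 2.8 | 2.5 |
| Week 16 | 0.30 | 2 | 1 | 8.4 | 7.5 |
| Week 52 | 0.20 | 3 | 0.5 | 4.2 | 1.15 |
| Week 52 | 0.20 | 3 | 1 | 8.4 | 2.3 |
| Week 52 | 0.30 | 5 | 1 | 21.0 | 5.8 |

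Over *d* from 0.05 to 0.30 and *s* from 0 to 1, the range is 0 to 8.4 days at Week 16 (*k* 1 to 2) and 0 to 21.0 days at Week 52 (*k* 1 to 5).

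**Step 4. Grams**

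The gram endpoint covers sponsor-provided low- and moderate-potency TCS, so the rescue product itself contributes nothing. What happens to background grams after rescue under rule #2 is unclear. SAP 6.8 applies the same assumptions as in the main gram analysis, without limiting them to missing values. One of those is that use continues at the pre-rescue amount. The text therefore allows either observed weights or the pre-rescue rate.

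**The case against.** The strongest reply is that the endpoint is days without *background* TCS, so a day with no background TCS is counted exactly as defined. Rescue is reported separately, by visit and by type (SAP 6.10.1), and SAP 6.8 is open about rescue tubes not being weighed. A count of days without any TCS would be a different endpoint. This is fair as far as the label goes. It does not explain why the main 16-week analysis treats every post-rescue day as use while the rule #2 analyses do not.

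A reader might infer that every rescue day becomes steroid-free and adds zero grams, so that the more-rescued arm must look more steroid-sparing. The documents do not support that:

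- Nothing says rescue replaces background TCS over the whole body. Protocol 7.7.2 allows low-potency TCS on thin-skin areas, and background use anywhere makes the day a use day.
- Zero grams is not established, because of the carried-over assumption in step 4.
- The documents do not say which arm is rescued more. If it is placebo, the shift runs against baricitinib and cannot create a false TCS-sparing claim. A reversed effect or disturbed dose ordering is not shown.

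It also stands that the Week 52 rule is inferred from SAP 6.3, since SAP 6.8 is silent.

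**Conclusion.** The point holds for the days endpoint, as a possible directional artefact of limited size. It affects the Week 16 secondary analysis and, if SAP 6.3 governs, the Week 52 main analysis. Rescue days without recorded background TCS count in favour of whichever arm has more of them.

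The per-patient bound of 14 days per course rests on a full-length course and complete replacement of background TCS. The arm-level figures rest wholly on assumed rescue rates, course counts and replacement shares. For grams, the supported finding is an ambiguity in the rule #2 wording, not a demonstrated bias.

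This is a low-priority improvement, worth making because it is cheap and removes an avoidable question from any TCS-sparing statement.

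**What to change.** In SAP 6.8:

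1. State that rule #2 governs the 52-week TCS analyses, and give the missing-diary convention for that time point.
2. For the rule #2 and 52-week analyses of days, count each day inside a recorded high- or ultra-high-potency TCS interval as a day with TCS use. Keep the background-only count as a labelled supportive summary.
3. Set a conservative convention for partial rescue dates.
4. For grams, say which post-rescue assumption carries into the rule #2 analysis. Label gram results as excluding rescue TCS and show rescue use by arm beside them.

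Rule #1 should not become the main 52-week gram analysis. It would discard observed tube weights from the first rescue onward. For a patient rescued at day 28, that is 364 − 28 = 336 of 364 days (92%) replaced by the pre-rescue rate, and rescue grams would still be missing.

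The cost is SAP wording and one merge of rescue records with the diary data. Protocol 7.7.2 and 7.7.5 already require topical rescue to be recorded, so no new data are needed. The day count needs dates rather than weights, and the main risk is that some dates are partial. SAP Version 5 serves the final lock, so if the change is made after the Week 52 lock the new count should be labelled supplementary.

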Descriptive statistics for drug accountability of topical low and moderate potency background medication provided by the sponsor will be presented, including the amount utilized throughout the 16-week and 24-week treatment period for 24-week interim analysis, and the entire 52-week treatment period for 52-week interim analysis. The total amount in grams for low and moderate potency, as well as the sum of both potencies will be summarized between visits. If a returned tube is not weighed in grams, the tube can be classified as partially used, fully used, unused, or unknown. Partially used background medication tubes will be considered to be 50% used, whereas fully used and unused will be considered as 100% and 0% used, respectively. When drug accountability is not performed for a particular tube of background medication or an answer of unknown is given for a tube which is not returned, that particular tube will not be included in the analysis.

For 24-week interim analysis, the main analysis on the total amount of background TCS throughout the entire 16-week treatment period will apply censoring rule #1. After patients who get rescued or discontinue investigational product, whichever is earlier, it is assumed that they would use the same amount of TCS as they did before. Analysis will be done via analysis of variance (ANOVA), with geographic region, baseline disease severity, and treatment as factors in the model. The secondary analysis will apply censoring rule #2 with the same assumptions as described above. For 52-week interim analysis, analysis will be done via ANOVA, with geographic region, baseline disease severity, and treatment as factors in the model.

- Mean gram quantity of background TCS used in Period 3 (tube weights)

For Long-Term Extension Period 3 (Week 52 through Week 104), the total amount utilized in grams for low and moderate potency will be summarized between visits (Week 52 through Week 56, Week 56 through Week 60, Week 60 through Week 64, and so on) as well as throughout the treatment period from Week 52 through 104 (Period 3). The total amount utilized will also be presented for the aforementioned visit intervals, irrespective of potency. Only descriptive statistics will be presented. No ANOVA model will be implemented. No censoring rule will be applied.

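### Leaving unaccounted tubes of background TCS out of the gram total scores them as 0 g, and no sensitivity analysis shows the effect

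*SAP*

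**What the plan says.** SAP Section 4.2.2 lists mean grams of background TCS over 16 weeks, from tube weights, among the other secondary endpoints. Of that group it says: "These are prespecified objectives that will not be adjusted for multiplicity". Section 6.8 draws the data from "drug accountability of topical low and moderate potency background medication provided by the sponsor" and defines the variable as a total: "The total amount in grams for low and moderate potency, as well as the sum of both potencies will be summarized between visits".

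Section 6.8 then sets these rules for use that was not weighed:

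- A returned tube without a weight is classed as partially used, fully used, unused or unknown. "Partially used background medication tubes will be considered to be 50% used"; full counts as 100% and unused as 0%. The class 'unknown' gets no value.
- "When drug accountability is not performed for a particular tube of background medication", or when a tube is not returned and the answer is 'unknown', "that particular tube will not be included in the analysis".
- After rescue or discontinuation of study drug, use is assumed to go on at its previous amount.

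The 16-week total is compared between arms by ANOVA with region, baseline severity and treatment. A secondary analysis under the second censoring rule keeps the same assumptions. The list of sensitivity analyses in Section 6.10.4 contains nothing on tube accountability.

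For the companion endpoint, days without background TCS, Section 6.8 says: "In case of missing values in the daily diary, it will be assumed that background TCS has been used".

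**The concern.** The rule removes a tube, not a patient or a visit interval. Nothing in Section 6.8 rescales the remaining total, imputes the tube or flags the total as incomplete. A patient with an unaccounted tube stays in the ANOVA with a total that is too low if that tube was used at all.

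The two TCS endpoints also lean in different directions. A missing diary day counts as use, which is cautious for a claim that baricitinib spares TCS. A missing tube counts as no use.

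At stake is the comparison of each dose with placebo on TCS quantity. If tubes are lost at different rates by arm, part of an apparent sparing effect, or the absence of one, could come from accountability. Section 6.8 does not plan to report unaccounted tubes by arm, so a reader of the results could not tell.

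**Working it through.** **Inputs.** From SAP Section 6.8: the total form of the variable, the rule that drops tubes, the 0%, 50% and 100% values, and the rule that carries use on after rescue. The plan gives no figure for tube loss or grams, so there is no stated result to reproduce. Assumed for illustration: a true placebo mean of 200 g, a true baricitinib mean of 200 g or 160 g, and 5% to 20% of each arm's grams in dropped tubes.

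**Step 1, one patient.** Six tubes with 30 g used from each: 6 × 30 = 180 g. With one tube dropped the plan records 5 × 30 = 150 g; with two dropped, 4 × 30 = 120 g. Scoring the same tubes as 0% used gives the same totals.

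**Step 2, arm means.** If a share m of true grams is in dropped tubes, the expected arm mean is the true mean × (1 − m). With true means B (baricitinib) and P (placebo), the expected difference is B(1 − m_B) − P(1 − m_P).

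| True P, B (g) | Loss in P, B | Difference under the rule (g) | True difference (g) |
|---|---|---|---|
| 200, 200 | 10%, 10% | 180 − 180 = 0 | 0 |
| 200, 200 | 5%, 15% | 170 − 190 = −20 | 0 |
| 200, 200 | 15%, 5% | 190 − 170 = +20 | 0 |
| 200, 160 | 5%, 5% | 152 − 190 = −38 | −40 |
| 200, 160 | 10%, 10% | 144 − 180 = −36 | −40 |
| 200, 160 | 20%, 20% | 128 − 160 = −32 | −40 |
| 200, 160 | 5%, 15% | 136 − 190 = −54 | −40 |
| 200, 160 | 15%, 5% | 152 − 170 = −18 | −40 |

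With equal true use, the relative difference at 5% versus 15% loss is 0.85/0.95 − 1 = −10.5%, whatever the true mean.

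**Step 3, carrying use on after rescue.** Take a patient rescued at Week 8 who truly used 100 g by then. With no loss the 16-week total is 2 × 100 = 200 g. With 10% of those grams in dropped tubes it is 2 × 90 = 180 g; with 20%, 2 × 80 = 160 g. The understatement is carried forward.

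**Step 4, counting dropped tubes as 100% used.** Assume accounted tubes are 80% used on average and dropped tubes were truly used like the rest, so that the share of tubes equals the share of grams. An arm with true mean T then shows T(1 − m) + (T/0.8)m.

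- True means 200 and 200, loss 5% and 15%: placebo 190 + 12.5 = 202.5 g, baricitinib 170 + 37.5 = 207.5 g, difference +5 g. The current rule gives −20 g; the truth is 0.
- True means 200 and 160, loss 5% and 15%: placebo 202.5 g, baricitinib 136 + 30 = 166 g, difference −36.5 g. The current rule gives −54 g; the truth is −40 g.

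In both cases the two scorings bracket the truth. Dividing each total by the share of tubes accounted for recovers it under the same assumption: 190/0.95 = 170/0.85 = 200 g.

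**The case against.** **The rule is narrow.** A reader might infer that every unreturned or unknown tube is dropped. The text does not say so. It drops tubes with no accountability and unreturned tubes answered 'unknown'. An unreturned tube reported as, say, fully used need not fall under it, and a returned tube classed 'unknown' has no explicit rule. This stands.

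**Nothing shows that lost tubes are the used ones.** It is tempting to argue that an unreturned tube was probably emptied. The documents offer no support. Two potencies are supplied, and Protocol Section 7.7.2 has patients step down and stop once lesions clear, so a mislaid tube may be nearly full. This stands too, but downward bias in the mean needs only some use.

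**The endpoints differ in kind.** A missing diary day is a yes/no value with an obvious cautious choice; a tube of unknown state is a quantity without one. The 50% and 100% values are coarse readings of tubes whose state was recorded, not imputations for absent data. It is therefore too strong to say that the plan treats identical missing data in opposite ways. The different leaning remains.

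**The size is hypothetical and the stakes are modest.** The loss rates are invented, and no reason is given why blinded arms should differ threefold. Grams are in any case a partial measure: Protocol Section 7.7.2 lets site-supplied TCS go unweighed where weighing is impractical, and rescue TCS is not weighed. Daily diary use is analysed separately and does not depend on tube return. All of this limits the importance of the point without removing the mechanism.

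**It is late.** SAP Section 6.16 reports the 24-week interim, which holds the 16-week gram analysis, as already conducted. A new main imputation rule would be post hoc. Interval-level imputation would also discard weighed tubes and ignore falling use over time, and a mean pooled across arms would dilute a true difference. That argues for a supplementary bounding analysis, not a replacement main analysis.

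**Conclusion.** The point holds in a limited form. As written, Section 6.8 gives an unaccounted tube the same 0 g as a confirmed unused one. This understates mean grams whenever such tubes had any use, and no planned analysis would reveal it.

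A reader might go further and infer that the rule favours baricitinib. The documents do not support that, because the direction of bias in the difference depends on loss by arm, which they do not give. With assumed losses of 5% and 15%, equal true use of 200 g shows as −20 g or +20 g, depending on which arm loses more. With equal loss of 5% to 20%, a true −40 g difference shrinks to between −38 g and −32 g. These figures assume the gram levels and loss shares; only the mechanism comes from the plan.

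The endpoint is an other secondary one outside the multiplicity scheme, so no primary or key secondary conclusion depends on it.

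**What to change.** 1. Report the number and share of unaccounted tubes by arm. This alone shows whether the issue matters.
2. Add to the ANOVA of total grams a sensitivity analysis that counts these tubes as 100% used, and label the current rule as the 0% bound. The pair bounds each arm's mean. It does not strictly bound the difference if lost tubes were used differently by arm, and the report should say so.
3. State how a returned tube classed 'unknown' is handled.
4. Optionally, add an analysis that divides each patient's grams by the share of dispensed tubes accounted for. It assumes that lost tubes were used like the others.

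For the 16-week data already analysed, label all of these as supplementary. The cost is SAP wording, modest programming and a wider stated range for one secondary endpoint. No new data collection is needed.
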